3.3.3.3 Definition of positive cavity

After the standard lumpectomy procedure, a positive cavity occurs when tumor is found in a therapeutic shave or during a re-excision.

4 PRODUCT DESCRIPTION

4.1 Intended use

The LUM Imaging System is a combination product consisting of the LUM015 imaging agent and the LUM Imaging Device. LUM015 is administered to the patient via intravenous injection 4 ± 2 hours prior to the first image recorded. The LUM Imaging Device is intended for use in vivo

following the excision of the main lumpectomy specimen to detect remaining cancer cells after breast conserving surgery.

4.2 Proposed indications for use

The LUM Imaging System is indicated for use in patients undergoing a breast conserving surgery (lumpectomy) to remove breast cancer. The LUM Imaging System is not indicated for those subjects receiving administration of blue (e.g. methylene blue, isosulfan blue) or green (e.g. indocyanine green) dyes for sentinel lymph node mapping procedures prior to the lumpectomy procedure. The LUM Imaging System is intended to be used whenever breast tissue is removed, histopathology evaluation of the tissue is the standard of care and/or it is essential that the tissue margins be examined for completeness of removal using standard surgical procedures. The LUM Imaging System is to be used *in vivo* following the excision of the main lumpectomy specimen to assist in locating residual abnormal tissue, therefore, facilitating tumor resection and potentially creating negative margins on the outermost surfaces of excised tissue.

4.3 LUM015 imaging agent

Lumicell engineered LUM015, a fluorescence-based imaging agent that accumulates within and around cells. In regions enriched with cathepsin enzymes, such as cancer cells, LUM015 is altered to fluoresce when illuminated with 649 nm light. In its nominal state, the fluorescence of LUM015 is suppressed by an internal quencher molecule (QSY21). The presence of cathepsin enzymes is not fully confined to cancer cells; hence, data from this study will help determine the cancer localization properties of LUM015. Once cathepsin enzymes cleave LUM015 at its amino acid backbone, the quencher is released and the fluorescent dye (Cy5) in LUM015 emits detectable fluorescence when it absorbs red light (**Figure 1**). The absorption and emission wavelength maxima for Cy5 are 649 nm and 670 nm respectively. LUM015 employs a fluorescent molecule with excitation and emission in the far red spectrum (> 600 nm wavelength) because in that range light can travel effectively through 1mm of tissue and tissue autofluorescence is minimal, allowing higher sensitivity due to lower background [14].

[figure not shown]

Figure 1: Schematic representation of LUM015.

Cathepsins are a family of enzymes that are involved in the degradation of the extracellular matrix to allow tumor growth and progression. These enzymes are upregulated in most human cancers and are also present in tumor-associated macrophages at the tumor's invasive front [15-19]. Platt et al. showed 60-fold higher cathepsin activity in breast cancer tissue than in healthy breast tissue [20]. Others report over-expression of cathepsin enzymes (B, K, L and D) in ductal carcinoma in situ as well as in invasive carcinomas (lobular and ductal) [16, 20-23]. Also, cathepsin B is typically over-expressed in inflammatory breast cancer, one of the most lethal forms of primary breast cancer. [24, 25]. The peptide sequence used in LUM015 is a pan-cathepsin substrate

LUMICELL CONFIDENTIAL

This document is confidential. Do not disclose or use except as authorized.

meaning that it will be cleaved by multiple enzymes of the cathepsin family. Because high activity of cathepsin enzymes is found in tumor cells and tumor associated macrophages surrounding the tumor at the invasive front, these enzymes provide an excellent marker for activating LUM015 at the tumor margin. The fluorescence of LUM015 is then induced and detected with the LUM Imaging System to identify cancer and cancer-related cells for immediate resection and to distinguish them from adjacent normal tissue.

4.4 LUM Imaging Device

The LUM Imaging Device consists of a computer control unit, monitor and light source mounted on a cart, and a hand-held optical head (LUM002/LUM003). The computer control unit collects, analyzes (based upon Lumicell's detection algorithm) and displays the resulting images gathered by the imaging head in real-time. The light source provides the illumination to excite the fluorescent dye present in LUM015. Light is transferred from the light source to the imaging head using an optical fiber bundle. The imaging head (Figure 2) was designed as a lightweight hand-held tool with a small profile to allow easy maneuverability and limited intrusiveness in the operating room. Because incisions and lumpectomy cavities can vary in size, Lumicell offers two options for the distal end diameter: LUM002, which has a 2.6 cm field of view along with a 3.1 cm outer diameter and LUM003, which has a 1.3 cm field of view and a 1.9 cm outer diameter. The surgeons will be able to choose which device size to use for any given surgery. These two device options were proven to be optically equivalent when imaging freshly excised breast tissue. Both imaging heads have a 45° bend at the distal end for examination of the walls of the lumpectomy cavity.

The hand-held optical head will be used within the sterile surgical field. Consequently, a sterile barrier assembly will be provided to cover the optical head, which comes into contact with both the surgeon and the patient's exposed tumor bed. The sterile barrier assembly is installed on the LUM Optical Head in the OR using sterile procedures.

[figure not shown]

Figure 2: (Left) Photo of the LUM Imaging System. (Right) Rendering of the LUM002 Optical Head scanning a lumpectomy cavity. The sterile cover over the device is not shown.

4.5 LUM decision software

LUMICELL CONFIDENTIAL

This document is confidential. Do not disclose or use except as authorized.

The LUM Imaging System is powered by Lumicell's proprietary decision software. The decision software uses an initial set of images acquired from the lumpectomy cavity after the main specimen is removed to set the tumor detection threshold. Then, while the surgeon scans the lumpectomy cavity walls with the LUM Optical Head, the decision software compares the intensity of an image against the tumor detection threshold and identifies whether a region of the image is suspected to contain tumor. Regions with fluorescence signal above the threshold are highlighted in the computer monitor for the surgeon to see in real-time; that is, there is no delay between the scanning of a region and the display of the results from that region. **Figure 3** shows the user interface and what the surgeon sees during scanning of the cavity walls. The decision software was developed and optimized during Phase A and Phase B of the Feasibility Study in breast cancer patients.

[figure not shown]

Figure 3: Screen shot of the user interface for the LUM decision software. Regions highlighted in red indicate areas suspect to have tumor.

4.6 Prior clinical studies with the LUM Imaging System in females with breast cancer

Following the designation of a device primary mode of action for the LUM Imaging System combination product by FDA, Lumicell and collaborators at MGH conducted a Feasibility Study in breast cancer patients under an Investigational Device Exemption (IDE). The Feasibility Study was divided into Phase A, Phase B and Phase C as described below, and all phases have been completed. A multi-site Pivotal Study is underway.

4.6.1 Summary of three phases of the Feasibility study (all completed)

- **Phase A (n=15 patients):** patients were administered with either no LUM015 (5 patients) or a dose of 0.5 mg/kg (5 patients) or 1.0 mg/kg (5 patients) 4 ± 2 hours prior to surgery and the LUM Imaging System was used to image the lumpectomy cavity before and after standard of care cavity shaves. Resected cavity shaves were also imaged. The imaging results were compared with pathology analysis of the cavity shaves. The endpoints were: (1) select a dose of LUM015 for Phase B; (2) determine the parameters of the tumor detection threshold; and (3) acquire safety data. No clinical action was taken by the surgeon based on the imaging results. A dose of 1.0 mg/kg was selected for Phase B and all subsequent clinical studies in breast cancer.
- **Phase B (n=45 patients):** the tumor detection threshold was implemented and the LUM Imaging System was used to scan the lumpectomy cavity to guide the removal of additional cavity shaves beyond the standard of care cavity shaves. The endpoints were: (1) evaluate and, if necessary, adjust the detection algorithm parameters, (2) adjust, if necessary, the protocol for the pivotal trial, and (3) collect safety data.

- **Phase C (multi-center evaluation, n=234 patients):** the tumor detection threshold and the LUM Imaging System was evaluated at multiple sites to (1) collect data to refine and verify the tumor detection algorithm, (2) complete hands-on training of surgeons and clinical staff that will be participating in the pivotal study, (3) identify and address any site-specific or user-specific issues for using the LUM Imaging System in breast cancer surgeries, and (4) collect safety and efficacy data.

Once a surgeon was trained in the use of the LUM Imaging System during Phase C of the Feasibility Study, the tumor detection algorithm was locked and this protocol has been initiated, the surgeon may begin enrolling patients for the pivotal study. Any surgeon or site that did not participate in the Phase C study will be required to undergo training and complete a modified proficiency program before starting enrollment for this pivotal study.

No serious adverse events were observed in both Phase A and Phase B of the Feasibility Study. The only adverse event noted in these two phases was a temporary blue discoloration at the injection site for LUM015 that resulted from extravasation of LUM015 during injection (see details in section 11.2) One patient enrolled in the Phase C study, with known hypersensitivity to contrast, experienced an anaphylactic reaction to the LUM015 injection. The patient recovered in <24 hours. No other related serious adverse events have been reported to date.

5 PIVOTAL STUDY DESIGN

5.1 Design Summary

This is a prospective, multi-center, two-arm, randomized, blinded clinical trial. All eligible subjects are injected with LUM015. All eligible subjects shall follow the day of surgery workflow illustrated in Figure 4.

[figure not shown]

Figure 4: Surgery workflow diagram. A detailed description of each step in the surgical workflow is provided in sections 5.2.3 - 5.2.9 below.

5.2 Methods

5.2.1 Establishing a patient in the electronic data capture system (EDC)

All consented patients should be entered into the electronic data capture system prior to surgery.

5.2.2 Collection of baseline Patient Reported Outcome Measures Data

After the patient has consented to participate and has consented to the collection of Patient Reported Outcome Measures (PROMs) Data, prior to surgery start, each enrolled subject should complete this baseline survey collecting data to support an evaluation of PROMs. Baseline evaluations will be electronically collected using the EDC system at any time after the patient consented to participate in the study and prior to their lumpectomy procedure. If the patient has not yet completed their survey at the time of injection, the study site should facilitate and remind the patient to complete their survey. The patient should not complete the baseline survey after the lumpectomy procedure. The completion of the survey is not a requirement to be enrolled into the study. Alternatives to electronic distribution of the surveys may be implemented.

5.2.3 LUM015 Injection and Randomization

LUMICELL CONFIDENTIAL

This document is confidential. Do not disclose or use except as authorized.

All consented and eligible patients will be injected with LUM015 at a dose of 1.0 mg/kg 4 ± 2 hours prior to the first image recorded with the LUM Imaging System during the lumpectomy procedure. After injection of Lumicell, prior to surgery, the clinical site must update the subject in the EDC to document the subject's status as 'enrolled'. Once a subject is classified as 'enrolled', the subject will be randomized to either the control arm or the treatment arm of this study. Although the subject is randomized at the time of enrollment, the randomization will not be revealed to the study team until after the standard of care lumpectomy is completed.

5.2.4 Main specimen resection

The surgeon shall remove the main specimen per standard of care with the intention of achieving grossly negative margins. See Appendix A for guidelines on how to handle and ink the main specimen. Before the main specimen resection is complete, the LUM Imaging Device shall be initialized and the sterile barrier shall be applied according to the Instructions For Use. A Study Worksheet provided by Lumicell shall be completed by the clinical site throughout the surgery to collect study related information.

5.2.5 Lumicell cavity initialization

The Lumicell cavity initialization shall be performed by recording images of the lumpectomy cavity walls per Instructions For Use manual to set the tumor detection threshold specific for that patient.

5.2.6 Standard of care shaves

Before removing standard of care comprehensive shaves or selective shaves (based on palpation of the main specimen or cavity walls, X-ray imaging of the intact main specimen, intraoperative frozen section pathology, or visual examination), the surgeon shall record a LUM image from all the orientations from which an SOC shave will be removed. At this time, the tumor detection algorithm will be "off" to allow fluorescence visualization and navigation of the lumpectomy cavity without highlighting of suspected tumor that may bias normal standard of care.

5.2.6.1 Prior to obtaining any SOC shaves or associated images, the surgeon shall document their intent of obtaining SOC shaves on the study worksheet.

5.2.6.2 When there is no tissue available to be removed from a given orientation (e.g., too close to skin or too close to the chest wall), no LUM image shall be collected from that orientation. This information must be documented.

5.2.6.3 The surgeon shall place the optical head at the cavity location where a standard of care shave will be taken, instruct the computer operator when to save the image and define the image orientation.

5.2.6.4 The surgeon shall take the standard of care shave from the imaged location.

5.2.6.5 The surgeon shall repeat steps 5.2.6.1-5.2.6.4 for all cavity location(s) where a standard of care shave will be taken.

5.2.6.6 The resected tissue(s) shall be handled and named according to the Appendix B.

Standard of care margin assessment will be made by pathology on all the tissue removed during the standard of care procedure. If a positive margin is determined, this subject will be included in

the positive margin population. The intent of the standard of care lumpectomy procedure is to achieve negative margins.

5.2.7 Randomization revealed

After completion of standard of care, the study coordinator (or other authorized person) shall log-in to the EDC system to reveal whether the patient will receive Lumicell image-guided intervention. Randomization will be performed at a ratio of 10:1; for every 10 patients undergoing Lumicell imaging directed tissue resection after standard of care (“to proceed”), 1 patient shall complete surgery following standard of care alone (“not to proceed”). The randomization is intended to mitigate potential surgeon bias, and the 10:1 ratio was chosen based on prior clinical studies that supported imaging agent efficacy trials.

5.2.8 Lumicell procedure (only patients randomized to the intervention arm)

After the standard of care is completed for patients randomized “to proceed” with the Lumicell intervention, the surgeon will scan the tumor bed to collect images of the cavity walls and remove therapeutic shaves as indicated by the LUM decision software (refer to the Instructions For Use manual for details). The software will automatically turn on the tumor detection algorithm to allow visualization and navigation of the lumpectomy cavity with highlighting of suspected tumor by the tumor detection algorithm.

5.2.8.1 When there is no tissue available to be removed from a given orientation (e.g., too close to skin or too close to the chest wall), no LUM image shall be collected from that orientation. This information must be documented.

5.2.8.2 The surgeon shall scan the cavity and generate images from each orientation. Images should be generated and saved for both LUM positive and negative results.

5.2.8.3 The surgeon shall take a Lumicell shave from each imaged location indicated as “positive” by the LUM decision software.

5.2.8.4 A maximum of two (2) Lumicell shaves may be taken from any one orientation. Additional Lumicell shaves beyond 2 per orientation will constitute a protocol violation.

5.2.8.5 The resected tissue(s) shall be handled and named according to the Appendix B.

If a shave is not taken when indicated by the LUM Imaging System or a Lumicell image is not recorded as described above, a protocol deviation will be recorded with exception as described in section 5.3.1. If images are not saved in all orientations, a protocol deviation will be recorded unless there is no enough tissue left to take a shave (see 5.2.8.1). The reason for not taking a shave when indicated by the Lumicell system shall be recorded.

5.2.9 Pathology

Pathology shall report on the following criteria for each sample of breast tissue excised during the surgery (main specimen and shaves). It is particularly important that the pathologist reports the tumor distance(s) to the specimen margin(s) for each specimen excised during surgery. Reporting on tumor distances to final margins alone will not allow for determination of study endpoints.

- Type of resection (e.g. lump or shave)
- Tissue dimensions (LxWxH)
- Tissue Weight (g), if available

LUMICELL CONFIDENTIAL

This document is confidential. Do not disclose or use except as authorized.

- Presence/absence of tumor (Invasive Lobular Carcinoma (ILC), Invasive Ductal Carcinoma (IDC), IDC with Ductal Carcinoma *in situ* (DCIS), DCIS only or any combination of these)
- tumor distance(s) to inked margin(s)
- tumor grade
- tumor size
- Other tissue type(s) present, including:
 - LCIS
 - Atypical ductal hyperplasia
 - Usual ductal hyperplasia
 - Inflammation
 - Fibroadipose only
 - Fibroadenoma
 - Papilloma
 - Dense Fibrous
 - Fibrocystic change
 - Apocrine metaplasia
 - Radial scar lesions
 - Biopsy site changes
 - Adenosis

The final margin assessment for a patient is based on the outermost surface. The pathologist will be blinded to the type of shave (Lumicell-guided or standard of care) when conducting the pathology evaluation.

5.2.9.1 Data collected from re-excision surgery

Margin assessment of the outermost resection surface from the initial surgery will be used to inform the surgeon whether a patient should receive re-excision surgery. Re-excision surgery data as well as pathology data from re-excision surgery will be collected. Data will be collected on patient-provider interaction and discussions when evaluating the recommendation for re-excision.

5.2.10 Follow-up

Subjects will be followed, and data collected as described in section 8.4.

5.2.11 Safety observations

All subjects will be observed to assess the safety of LUM015 with standard preoperative, intraoperative and postoperative monitoring after receipt of the LUM015 injection. The subject will have a final safety assessment at the first post-operative visit, where a blood draw will occur, and lab values evaluated for clinically significant values that differ from the subject's baseline values. All subjects will continue their enrollment and be followed in the study until their medical team determines that no further surgical intervention is required.

5.2.12 Other general procedures and injection of LUM015

For subjects with non-palpable tumors, an ultrasound, mammogram or MRI-guided localization procedure may be performed prior to or the same day as the surgery. Also, patients having a sentinel lymph node (SLN) mapping procedure may be injected with the radiotracer Technetium-

99 (Tc-99) per standard of care. LUM015 may be injected before or after any of these procedures, as long as the injection occurs 4 ± 2 hours prior to the first image recorded.

Prior to the surgery, the LUM Imaging System will be positioned in the operating room and an initialization procedure will be conducted to ensure that the performance parameters of the device are within defined specifications. If during the initialization procedures, the performance parameters are outside the defined specification, the user is prompted to discontinue use of the device. If the error cannot be fixed within a reasonable time in the operating room, these patients will receive standard of care treatment and will not be imaged with the LUM Imaging Device. These patients will be followed and monitored for safety the same way as those patients that undergo imaging with the LUM Imaging Device. The patients that are not imaged with the LUM Imaging Device will be included in the safety cohort and will count towards device failure rate.

To avoid excessive tissue resection based on LUM015 signal, surgeons are not to take more than 2 therapeutic shaves in a given orientation.

5.3 Lumpectomy specimen and cavity walls orientation nomenclature

Throughout this protocol, reference is made to the orientation of the main specimen, the SCMs and the lumpectomy cavity walls. When a lumpectomy is performed, there are typically 6 surfaces defined for orienting the main specimen and SCMs for final margin assessment. **Figure 5** shows a schematic representation of the nomenclature for the lumpectomy cavity margins for a right-sided breast lumpectomy, showing 5 orientations. The sixth orientation (not shown in the figure) is the “anterior” margin. Shaved cavity margins removed under the guidance of the LUM Imaging System will be named “therapeutic shaves” to distinguish them from standard of care SCMs. Please see Appendix B for the guidelines on naming the resected tissue. Excised tissue should be stitched and inked according to Appendix A.

[figure not shown]

Figure 5: Schematic representation of the surfaces of the lumpectomy cavity walls (white circle). The posterior margin is nearest the fascia of the pectoral muscle. The anterior margin (not shown) is nearest the skin.

5.3.1 Guidance on removing therapeutic shaves

Therapeutic shaves should be removed anytime the LUM Imaging System indicates signal above the threshold (LUM positive signal shown in red in the computer screen). However, if there is not enough tissue to be removed (e.g. too close to skin, too close chest wall), a Lumicell image shall not be recorded and a therapeutic shave shall not be removed. This should be documented. Protocol deviations for not imaging and for not obtaining a therapeutic shave will not be issued when tissue is not obtained because there is not enough tissue to be removed.

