4.11.3 Missing and spurious data

During LUM-guided imaging, when there is not enough tissue to be removed (e.g. too close to skin or too close to the chest wall) no LUM image shall be recorded because it does not generate an actionable result.

In the case where the LUM Imaging System indicates that a therapeutic shave needs to be removed but the surgeon decides not to follow this guidance, the reason for not doing so will be recorded in the patient's CRF or during imaging. These instances are considered as a protocol deviation. There are other cases when the LUM-guide shave reach the protocol limit of 2 guided shaves per orientation, so a third guided shave will not be performed. In these cases, the data will be included in the performance evaluation as is; that is, because these will not generate a LUM-guided shave they will not be evaluated as removing cancer or converting positive margins to negative margins. However, they will be evaluated for the per-tissue sensitivity and specificity calculation according the hierarchical approach described in section 3.2.2.

In occasions, a cavity image may be recorded from an unintended region or the image may be deemed as low quality (blurry, out of focus, etc.). For example, the surgeon realizes that he/she placed the device in the wrong location within the cavity after recording an image. Since the LUM software does not allow to overwrite saved images, the error images will be labeled as "image error delete", and the image will be excluded from the analysis.

Other specific cases will be handled as described below.

- a. When a patient was prescribed Letrozole adjuvant therapy prior to surgery, the patient will be removed from the device performance evaluation (major protocol deviation) in the per-protocol analysis but will be included in the mITT population for primary analysis.
- b. When the time from injection of LUM015 to initial imaging time is greater than 6 hours due to unplanned surgical delays, the patients will be removed from the device performance evaluation (major protocol deviation) in the per-protocol analysis but will be included in the mITT population for primary analysis.
- c. For the re-excision rate endpoints, all patients undergoing a re-excision will be included in the analysis.
- d. In the case of a therapeutic shave taken but no image saved before the shave was removed, the shave will be excluded from analysis but will be included in the estimation of final margin.

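### Protocol 5.3.1 lets a LUM-positive site go unrecorded on a tissue judgement made after its result is displayed, which could inflate specificity by an unknown amount

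*Protocol*

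**What the plan says.** Protocol 5.3.1 starts from the signal: "Therapeutic shaves should be removed anytime the LUM Imaging System indicates signal above the threshold". The exemption follows as a qualification. Where tissue is insufficient, "a Lumicell image shall not be recorded and a therapeutic shave shall not be removed", the circumstance is to be documented, and deviations for not imaging or not shaving "will not be issued when tissue is not obtained because there is not enough tissue to be removed". Protocol 5.2.8 makes an untaken indicated shave or a missing image a deviation, but refers to 5.3.1 for the exception.

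In the intervention arm the result is visible during the scan. Protocol 5.2.8 says: "The software will automatically turn on the tumor detection algorithm to allow visualization and navigation of the lumpectomy cavity with highlighting of suspected tumor". Protocol 4.5 adds that "there is no delay between the scanning of a region and the display of the results from that region". Protocol 5.2.8.2 asks for the results in both directions: "Images should be generated and saved for both LUM positive and negative results".

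Elsewhere the no-tissue rule does not mention the signal. Protocol 5.2.8.1 says that for an orientation with nothing left to remove, "no LUM image shall be collected from that orientation". Protocol 15.4.6 agrees, as does SAP 4.11.3: "no LUM image shall be recorded because it does not generate an actionable result".

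SAP 4.11.3 treats two other kinds of unshaved LUM-positive site differently. Where the surgeon declines the shave, or the limit of two shaves per orientation has been reached, the site stays in the per-tissue sensitivity and specificity calculation and is scored by the truth-standard hierarchy.

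**The concern.** Entry into a diagnostic accuracy table should not depend on the test result. Under 5.3.1 it can. The operator sees a positive display, which calls for a shave and so raises the question of whether there is tissue to take. If the answer is no, the site is not recorded. A negative display calls for no shave and gives no comparable reason to ask, so an image of a similar wall may simply be saved. Most such images would be scored as true negatives.

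Specificity is one of three co-primary endpoints that must all succeed. Its goal is 60% and the planning value is 65%. Selective loss of positives would remove mainly false positives and push the estimate upward.

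The missing shave does not make such a site unscorable. The hierarchy in Protocol 15.2 and SAP 3.2.2 falls back to re-excision and then to the margin of the tissue already removed, and SAP 4.11.3 uses that route for the other untaken shaves.

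**Working it through.** **1. The plan's own figure.** Protocol 15.3.2 gives 1021 truth-standard negatives, specificity 65% against 60%, exact binomial, one-sided 2.5%, power 90%. At n = 1021 the smallest rejecting count is 644. The exact type I error is 0.0238 and the power is 0.907, so the stated figure reproduces.

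**2. Who would be dropped.** SAP 4.3.2 plans on 96% truth-negative sites, sensitivity 60% and specificity 65%. Per site:

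- false positives: 0.96 × 0.35 = 0.336
- true positives: 0.04 × 0.60 = 0.024
- false-positive share of all LUM-positive sites: 0.336 / 0.360 = 93%

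Dropped positives would therefore be mostly false positives.

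**3. Effect on specificity.** Let s be true specificity and f the share of false positives left unrecorded, with all negatives kept. Apparent specificity is s / (s + (1 − s)(1 − f)). The documents give no value for f, so the values below are assumptions. At s = 0.60 the denominators are 0.992, 0.980 and 0.960 for f = 2%, 5% and 10%. The false-pass columns apply the exact binomial test against 60% to the negatives that remain.

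| f (assumed) | Apparent specificity | Negatives left of 1021 | False pass, from 1021 | False pass, from 1800 |
|---|---|---|---|---|
| 0 | 60.0% | 1021 | 2.4% | 2.3% |
| 2% | 60.5% | 1013 | 4.8% | 5.9% |
| 5% | 61.2% | 1001 | 11.3% | 17.0% |
| 10% | 62.5% | 980 | 34.7% | 55.0% |

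The 1800 column uses the yield in Protocol 15.3.3: 1021 / 152 = 6.72 negatives per patient, times 268 patients.

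**4. Clustering.** The SAP tests with GEE, not the binomial. A simple design effect with the SAP's ICC of 0.22 is 1 + (6.72 − 1) × 0.22 = 2.26. With it, and a normal approximation, the false-pass probability is about 8% and 19% (f = 5% and 10%) from 1021 negatives, and about 10% and 30% from 1800. The excess is smaller but remains well above 2.5%.

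**5. Effect on sensitivity.** If true positives are lost at the same rate, a sensitivity of 60% with f = 10% reads 0.54 / (0.54 + 0.40) = 57.4%.

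**6. A related route.** SAP 4.11.2 calls an orientation positive if any of its images is positive. If only the positive image goes unsaved and the others are negative, a false positive becomes a true negative. Apparent specificity is then s + (1 − s)f, which is 64% at s = 60% and f = 10%. Protocol 5.2.8.1 read literally would bar those other images too.

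**The case against.** A reader might infer that the plan itself keeps negative images of no-tissue walls while discarding positive ones. The documents do not say so. Protocol 5.2.8.1 and 15.4.6 and SAP 4.11.3 bar any image where tissue is lacking, whatever the signal. In 5.2.8 that rule is listed before the scan-and-save step, and a rule applied that way does not bias specificity. The asymmetry is an inference about practice.

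Nor does SAP 4.11.3 single out positive sites for removal: its thin-tissue sentence does not mention them. Thin tissue is also not the only ground for exclusion, since erroneous images are dropped and SAP 4.9 and 4.10 allow removal after adjudication.

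There are safeguards. Lack of tissue must be documented, and failing to save all orientations for any other reason is a deviation. Protocol 5.2.6.2 already has missing tissue documented with the algorithm off, though only for orientations with a planned standard-of-care shave and before that shave is taken.

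Large values of f are hard to reach. If false positives were spread evenly over six walls and only the anterior and posterior walls were affected (both assumptions), f = 10% would need 0.10 / (2/6) = 30% of the false positives on those two walls to go unrecorded. Phase C specificity was 70% (68% to 73%), SAP 4.5 states power above 99%, and lost true positives work against the sponsor on sensitivity.

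All of this limits certainty about size and occurrence. What stands is that 5.3.1 reads signal-first, the display is live, the order of judgement is not fixed, and no planned analysis bounds the effect.

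**Conclusion.** The plan permits a result-dependent exclusion from a co-primary analysis and does not provide a way to measure it. That rests on the text of Protocol 5.3.1 and the waiver in 5.2.8, set against the signal-neutral wording elsewhere. That specificity is actually inflated is possible but not shown. It needs the tissue judgement to be prompted mainly by positive signals, and the documents give neither that pattern nor a rate of insufficient tissue.

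The consequence depends on where true specificity lies. At the 60% goal, an assumed loss of only 2% of false positives roughly doubles the binomial false-pass probability from 1021 negatives (2.4% to 4.8%), and 10% takes it to about 35%. Near the Phase C value, success would rarely turn on this, but the reported estimate could still be high: at a true 70%, f = 10% reads 0.70 / (0.70 + 0.27) = 72.2%. This is a cheap improvement worth making, not evidence that the specificity result is invalid.

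**What to change.** **Protocol.** Reconcile 5.2.8.1 with 5.3.1 so that tissue availability for each orientation is entered on the worksheet before the detection algorithm is turned on. Save and analyse the LUM result for every orientation declared available. If no shave follows, score the saved result by the existing hierarchy (re-excision, then prior margin), as SAP 4.11.3 does for other untaken shaves.

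**SAP.** SAP 1.1 refers to 406 patients enrolled, so a worksheet change may come too late for most or all of the data. For those patients, tabulate the documented no-tissue orientations, by wall and by signal where it was noted. Add an analysis of sensitivity and specificity that counts no-tissue positives by the hierarchy. Where the signal is unknown, use a tipping-point analysis: report how many unrecorded false positives would bring the lower specificity bound to 60%, and compare that with the number of documented no-tissue orientations.

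**Cost.** One worksheet field, the saved images for affected orientations and a little more analysis. Specificity may read slightly lower, and some added sites will rest on the prior margin, the lowest tier of the truth standard. Only recording and analysis change; what tissue is removed does not.
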